6.2. Scientific Rationale for Study Design

Double-blind, randomized, placebo-controlled study designs provide unbiased estimates of efficacy and safety. Withdrawal of all concomitant analgesic medication during the Screening Period is expected to reduce intersubject variability in treatment response [Katz 2005; Katz 2015; Data on file] Acetaminophen will be provided as rescue medication. The three-month duration of treatment is considered sufficient to identify clinically important and durable pain relief.

Only masked versions of the protocol will be provided to study sites. The masked versions will obscure the probability of receiving placebo, the treatment period, and the randomization criteria (Section 7.1). Masking is expected to reduce variability in treatment response and to reduce the response to placebo.

6.3. Justification of Dose

The planned dose levels of NYX-2925 are 50 mg and 100 mg per day. Preliminary analysis of the data from the previous Phase 2 study of NYX-2925 in fibromyalgia suggest that after treatment with 20 mg for two weeks followed by 200 mg for two weeks, clinical effects were observed (see Section 4). Over an extended time pDPN tends to become a chronic centralized pain condition [Schreiber 2015, Tesfaye 2013], similar to fibromyalgia. In the Phase 2 study of NYX-2925 in pDPN, the most consistent effects among the pre-planned and post-hoc analyses were observed after administration of 50 mg, and there were also effects seen at the 200 mg dose, although less consistently. The adverse event profile revealed no differences to placebo across the entire dose range in either study. Based on the presumed mechanism of action of NYX-2925, there is no reason to suspect that the dose range for fibromyalgia should be different to that for pDPN. To date no dose level between the four-fold range of 50 mg to 200 mg has been studied in a patient population. Therefore, to obtain a more precise understanding of the dose-response relationship within this range, an additional dose of 100 mg has been selected along with the dose strength of 50 mg to be compared to placebo for the current trial. In the Phase 1 single and multiple ascending dose safety, tolerability and pharmacokinetic study, the PK of NYX-2925 were dose proportional over the dose range tested (50 – 1200 mg). The coefficient of variation (CV%) for exposure remained relatively low across the range (14.0% - 31.5%). Furthermore, a high-fat, high-caloric meal decreased the rate of absorption (delayed T_{max}) and lowered C_{max} by 10%, but had no impact on the extent of exposure (AUC values were comparable), suggesting NYX-2925 can be administered with or without food.

7. SELECTION AND WITHDRAWAL OF SUBJECTS

7.1. Subject Inclusion Criteria

Inclusion Criteria: Screening

Inclusion Criteria: Screening

Subjects must meet ALL the following criteria to be enrolled in this study:

1. An Institutional Review Board approved written informed consent and privacy language (Health Insurance Portability and Accountability Act (HIPAA)) authorization must be obtained from the subject prior to performing any study-related procedures. This study may employ electronic informed consent. Electronic or digital signatures (compliant with 21 CFR § 11 regulations for collecting and storing digital signatures) may be captured indicating the patient's willingness to participate in the clinical trial. The use of electronic informed consent supplements the interaction between the participant and the research staff, and it provides an opportunity for remote conduct of study activities in the setting of the COVID-19 Health Emergency.
2. Subject provides separate consent to being included in a research subject database.
3. Subject is ≥ 18 and ≤ 75 years of age.
4. Subjects must meet the following 3 conditions described in the 2016 American College of Rheumatology criteria for fibromyalgia [[Wolfe 2016](#)]:
 - a) Widespread Pain Index ≥ 7 and Symptom Severity Score ≥ 5 , or the Widespread Pain Index is 4 to 6 and the Symptom Severity Score is ≥ 9 .
 - b) Symptoms have been present at a similar level for ≥ 3 months; and
 - c) Pain is generalized and present in at least 4 of 5 regions.
5. Subject has a history of fibromyalgia that was diagnosed >1 year prior to Screening.
6. Subject reports at least moderate pain over the last week, as assessed by PGI-S at Visit 1.
7. Subject agrees to use only rescue medication provided treatment as needed for breakthrough pain related to fibromyalgia.
8. Subject agrees not to initiate or change any non-pharmacologic interventions (including normal daily exercise routines, chiropractic care, physical therapy, psychotherapy, and massage therapy) during the study. Any ongoing non-pharmacologic intervention must be stable for at least 30 days prior to screening.
9. Subject has a body mass index (BMI) ≤ 40 kg/m².
10. Subject's calculated creatinine clearance is ≥ 60 mL/minute (Cockcroft-Gault formula).
11. Absence of impaired hepatic function characterized by a previous known diagnosis of chronic liver disease, and/or the presence of abnormal serum total bilirubin (TBL), or alanine transaminase (ALT), aspartate transaminase (AST), or alkaline phosphatase (ALP) >1.5 x upper limit of normal (ULN) at screening.

12. Except as noted in criteria 10 and 11, subject's clinical laboratory values are within normal limits or deemed not clinically significant by the Investigator.
13. Female subjects of child bearing potential with a negative pregnancy test prior to entry into the study and who are practicing a highly effective method of birth control (e.g., oral or parenteral contraceptives, intrauterine device, barrier [condom and spermicide], abstinence) and who do not plan to become pregnant, breastfeed, or donate ova during the course of the study and for 28 days after the final administration of investigational product.
14. Male subjects should use a highly effective method of birth control and refrain from sexual activity with female sexual partners who do not use a highly effective method of birth control during the study. Male subjects who are not surgically sterilized for at least 90 days prior to screening and sexually active with female partner(s), must agree to use barrier contraception (condom with spermicide) during the study. Subjects must agree to refrain from sperm donation during the study and for 90 days after the final administration of investigational product.
15. Subject has not participated in an interventional study for at least 30 days or has not taken investigational study medication for a period of at least 5 half-lives of the study medication, whichever is longer. Agrees not to participate in another interventional study while on treatment. Eligibility will be reviewed during the study via sponsor participation in a research subject database.
16. Subject has the ability to understand the requirements of the study, abide by the study restrictions, as well as concomitant medications exclusions and agrees to return for the required assessments.

7.2. Subject Exclusion Criteria

Exclusion Criteria:

Subjects who meets ANY of the following criteria will be excluded from the study:

1. Lifetime history of any psychotic and/or bipolar disorder.
2. Subjects with uncontrolled major depressive disorder or generalized anxiety disorder, in the investigator's opinion. (subjects may have been on a stable protocol allowed medication for greater than 60 days prior to screening) or are not expected to remain stable for the duration of the study.
3. Pain due to diabetic peripheral neuropathy, post-herpetic neuralgia, traumatic injury, prior surgery, complex regional pain syndrome, or other source of pain that, in the investigator's opinion, would confound or interfere with the assessment of the subject's fibromyalgia pain or require excluded therapies during the subject's study participation.
4. Pain due to concurrent autoimmune, infectious, or inflammatory disease such as rheumatoid arthritis, systemic lupus erythematosus, ankylosing spondylitis, psoriatic arthritis, inflammatory bowel disease, or other chronic widespread pain condition(s) that may confound fibromyalgia pain reporting.
5. Any impairment, activity or situation that, in the judgment of the Investigator, would prevent satisfactory completion of the study protocol.

6. An untreated endocrine disorder that may confound fibromyalgia assessments.
7. History of severe renal impairment defined by currently receiving hemodialysis or peritoneal dialysis or has undergone a previous renal transplant.
8. Known history of significant cardiovascular condition, such as myocardial infarction within the past year, or moderate to severe congestive heart failure (New York Heart Association [NYHA] Class III and IV); evidence of current uncontrolled cardiac arrhythmias, angina; or electrocardiographic evidence of acute ischemia or clinically significant conduction system anomalies; QTcF >450 msec (males) or >470 msec (females); or uncontrolled hypertension characterized by resting systolic blood pressure >160 mm Hg or resting diastolic >100 mm Hg, or clinically significant hypotension in the judgement of the Investigator as characterized by resting systolic blood pressure <90 mm Hg or resting diastolic blood pressure <60 mm Hg accompanied by symptoms such as lightheadedness, dizziness, and profound fatigue or signs such as irregular heartbeat.
9. Resting pulse rate <45 bpm or >95 bpm.
10. History of Huntington's disease, Parkinson's disease, Alzheimer's disease, multiple sclerosis, or a history of seizures (with the exception of childhood febrile seizures), epilepsy, or stroke.
11. Subject has evidence of any clinically significant, uncontrolled gastrointestinal, endocrinologic, hematologic, immunologic, metabolic, urologic, pulmonary (including uncontrolled, obstructive sleep apnea), neurologic, dermatologic, and/or other major disease (exclusive of fibromyalgia) that may interfere with study participation, as assessed the investigator.
12. Positive serology test for human immunodeficiency virus (HIV) or hepatitis B or C infection, or other ongoing infectious disease that the investigator considers clinically significant.
13. Concomitant use of protocol specified prohibited medications from which subject is unable to wash-out (see Section 8.7 of the protocol for Concomitant Medications Restrictions).
 - a. Washout from excluded medication allowed only if the Investigator deems it medically appropriate.
 - b. Washout should be completed during screening, with the last dose being at least two (2) weeks prior to randomization (See Section 15.1 of the protocol for Disallowed Analgesic and Other Medications).
14. Sensitivity or allergy to N-methyl-D-aspartate receptor ligands including ketamine, esketamine, amantadine, dextromethorphan, memantine, methadone, dextropropoxyphene and/or ketobemidone.
15. Use of NMDAR-binding drugs (e.g., ketamine, esketamine, amantadine, dextromethorphan, memantine, methadone, dextropropoxyphene, and/or ketobemidone) within 30 days prior to dosing or during the study.
16. Sensitivity to or intolerance to acetaminophen or associated formulation components.

17. Current or recent (within 12 months of screening) history of a substance use disorder including cannabinoid and/or alcohol use disorder as determined using the standard MINI version 7.0.2 for DSM-5™.
18. a. Positive urine drug screen for benzodiazepines or opioids inconsistent with current prescriptions, psychoactive cannabinoids (e.g., marijuana, THC) inconsistent with subject reported use, PCP, cocaine, or amphetamines at Visit 1.
b. Positive urine drug screen for benzodiazepines inconsistent with protocol specified allowed prescriptions, psychoactive cannabinoids (e.g., marijuana, THC) inconsistent with subject reported use, opioids, PCP, cocaine, or amphetamines at Visit 2.
19. Hypersensitivity or intolerance to multiple medications, in the opinion of the Investigator.
20. Meets the criteria for suicidal intent, plan and/or behavior by scoring 3 or 4 on Questions 2 or 13, or 2 or higher on any Question 1a (only if 1b is coded YES), 3, 4, 5, 6, 7, 8, 9, 10, 11, 12, or 14 based on the S-STS or who is at significant risk to commit suicide, as assessed by the investigator, at Visit 1 or Visit 2.
21. Planned surgery during study participation.
22. Active malignancy or a history of malignancy (except for treated non-melanoma in-situ skin cancer) within 5 years of screening.
23. Subject has filed for a disability claim or has any pending worker's compensation litigation.
24. Employee, contractor, or volunteer of the study site, CRO, or Aptinyx, or relative of any employee, contractor, or volunteer of the study site, CRO, or Aptinyx or previous randomization into any clinical trial for NYX-2925.
25. Any condition, including serious medical conditions, that could interfere with the ability of the subject to participate in the study or could confound study assessments.
26. History of severe infection with COVID-19 requiring hospitalization, treatment with oxygen or mechanical ventilation, that may interfere with study participation, as assessed the investigator.
27. Any subject with a medical history of COVID-19 infection (positive test) within the last two (2) months, or current symptoms consistent with COVID-19 infection (not tested), e.g. loss of smell, sore throat, cough or fever (2 or more symptoms at the same time), as assessed by the investigator.

Inclusion Criteria: Randomization

Daily pain scores and diary compliance will be transferred into the interactive response technology system, which will be used to assess the criteria for randomization. Subjects whose mean of the daily average pain intensity score during the preceding seven (7) days is within the protocol-defined algorithm and with adequate compliance with daily diary completion will be eligible for randomization.

Waivers to the inclusion or exclusion criteria will **NOT** be allowed.

7.3. Screen Failures

Subjects who sign and date the informed consent form, but who fail to meet the inclusion and do not meet any exclusion criteria, will be considered screen failures. The reason(s) for screen failure must be documented by the Investigator. Screen failures may be rescreened, at the Investigator's discretion and will receive a new subject number. Subjects who are randomization ineligible, as determined by IRT, may not be rescreened.

7.4. Subject Withdrawal Criteria

Subjects who withdraw from the Treatment Period will not be replaced. Any subject may withdraw consent at any point during the study. The Investigator may discontinue a subject at any time if it is deemed medically appropriate or for subject noncompliance with study requirements. Subjects who terminate early should return to the clinic for the Early Termination Visit. Subjects may be withdrawn from the study if any of the following criteria are met:

- Occurrence of an adverse event, intercurrent illness, or laboratory abnormality that, in the opinion of the Investigator, warrants the subject's permanent withdrawal from the study for subject safety
- Lack of efficacy
- Subject withdraws consent
- Subject noncompliance
- Lost to follow-up
- Pregnancy
- Sponsor termination of study
- An individual stopping criterion is met
- Other
- Other: COVID-19

7.5. Methods of Birth Control

If heterosexually active and of childbearing potential, female subjects must agree to consistently use a highly effective method of birth control starting at Visit 1, continuing throughout the study, and for 28 days after the last dose of study drug. Methods of highly effective birth control include:

- Oral or parenteral contraceptives
- Intrauterine device (either hormonal or nonhormonal type acceptable)
- Barrier
- Abstinence

Female subjects must agree not to plan to become pregnant or breastfeed starting at Visit 1, during the study and for 28 days after the last dose of study drug. Female subjects must refrain

from donating ova during the study period and for 28 days after final administration of investigational product.

Male subjects must use a highly effective method of birth control and refrain from sexual activity with female sexual partners who do not use a highly effective method of birth control starting at Visit 1 through the last dose of study drug. Male subjects who are not surgically sterilized for ≥ 90 days prior to Visit 1 and are sexually active with a female partner must use a condom with spermicide during the study. Male subjects must refrain from sperm donation during the study and for 90 days after the final administration of investigational product.

All pregnancies (female subjects and female partners of male subjects) occurring during the study must be followed for information regarding the course of pregnancy, delivery, and condition of the newborn. Follow-up should be provided by the investigator to the Sponsor-designated Medical Monitor in a timely manner. When the newborn is healthy, further follow-up is not necessary.

7.6. Accurate Pain Reporting and Placebo Response Reduction Training

Prior to recording their first pain score in the handheld diary, each subject will undergo training on Accurate Pain Reporting (APR®) and Placebo Response Reduction (PRR®) via an electronic learning management system, aLearn® [Analgesic Solutions, Wayland, MA]. Subjects will repeat refresher training at subsequent site based study visits, with the exception of the final visit. Refresher training may also be completed remotely via aLearn® at Visit 3, or anytime, per Investigator discretion.

8. STUDY TREATMENT

8.1. Dosing and Administration

This is a double-blind study. Subjects, study personnel and the Sponsor will be blinded to study treatment.

Subjects will be dispensed study drug according to the randomization schedule. A four-week supply of study drug will be dispensed at Weeks 0 (baseline), 4, and 8. Subjects will be instructed to take one capsules of study drug once daily by mouth. The first dose of study drug will be taken in the clinic during the Visit 2 (Week 0). Subjects will be instructed to take study drug once daily throughout the study.

Subjects will be randomized to NYX-2925 50 mg, NYX-2925 100 mg or placebo by mouth, once daily.

Subjects will be dispensed three (3) bottles of acetaminophen to be used as rescue medication at Visit 1. Rescue medication will be dispensed/re-dispensed at the visits identified in [Table 3](#). Rescue medication will consist of 100 count bottle, 500 mg tablets of acetaminophen. Subjects will be instructed to take no more than 3 g/day (one to two 500 mg tablets every 6 hours as needed) for pain associated with fibromyalgia. Rescue medication will be provided by the Sponsor. Use of rescue medication should be reported daily via the study issued- handheld device.

8.2. Study Drug Description, Appearance, Packaging, and Labeling

NYX-2925 is a small molecule, [REDACTED]

[REDACTED] that will be provided as capsules for oral administration in a strength of 50 mg and 100 mg NYX-2925 per capsule. Matching placebo capsules will also be provided.

[REDACTED]
[REDACTED]
[REDACTED]
[REDACTED]

The study drug will be provided in bottles. The labels will include “NYX 2925 Oral Capsules or Placebo,” capsule count, bottle number, storage conditions, protocol number, Sponsor name, and investigational use statement. Bottles of study drug will be dispensed at Visit 2/Week 0, Visit 4/Week 4 and Visit 5/Week 8 will include 32 capsules of NYX-2925 50 mg, NYX-2925 100 mg or matching placebo capsules according to the randomization schedule.

Acetaminophen rescue medication will be provided in 100 count bottles containing 500 mg tablets of acetaminophen. The labels will include “Acetaminophen 500 mg tablets”, bottle number, protocol number and Sponsor name. Subjects will be instructed to take no more than 3 g/day (one to two 500 mg tablets every 6 hours) as needed for pain related to fibromyalgia. Subjects will be dispensed three (3) bottles of acetaminophen to be used as rescue medication at Visit 1. Additional bottles of rescue medication will be dispensed as needed.

The Sponsor will provide investigative sites with sufficient amounts of study drug and rescue medication to conduct the study.

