proportional over the dose range tested and showed minimal accumulation following once daily dosing for seven days. A high-fat, high-caloric meal decreased the rate of absorption and lowered peak plasma concentration by 10%, but had no impact on the extent of exposure, suggesting that the compound may be administered with or without food. The majority (approximately 60% to 70%) of the administered dose was eliminated as unchanged NYX-2925 in the urine. Central nervous system exposure was confirmed, and CSF concentrations increased proportionally as the dose increased.

NYX-2925-1003 was a Phase 1 randomized, double-blind, placebo-controlled, crossover study of the effects of NYX-2925 on sleep architecture in healthy male volunteers. Preliminary PD results from this study indicate that a single oral dose of 100 mg NYX-2925 in healthy subjects increased sleep efficiency (total sleep time) as well as non-rapid eye movement (NREM) sleep time without affecting rapid eye movement (REM) sleep or inducing daytime drowsiness in the placebo/NYX-2925 arm.

NYX-2925-1004 was a Phase 1 double-blind, randomized, sponsor-open, parallel, placebo-controlled exploratory study to assess the effect of multiple dose levels (10, 50, or 200 mg) of NYX-2925 on the brain function of healthy volunteers as measured by EEG and event-related potentials (ERPs). NYX 2925 was shown to acutely enhance NMDAR-dependent mismatch negativity (MMN) at the lowest dose tested (10 mg single dose) and quantitative electroencephalogram (EEG) changes along with auditory long-term plasticity changes were seen across the dose levels. This study also showed auditory long-term plasticity changes 3 and 7 days after a single dose.

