Study Period	Screening		Baseline		Treatment Period		
	Study Week	1 to 4 weeks ^a (-28 to -1)	Week 0 ^d (1 ±2)	Week 2 (14 ±2)	Week 4 (28 ±4)	Week 8 (56 ±4)	Week 12 ^b (84 ±4)
Study Visit	Visit 1	Visit 2	Visit 3 ^v	Visit 4	Visit 5	Visit 6	
Record average pain intensity ^m and rescue medication use over past 24 hours at bedtime for each day	X	X	X	X	X	X	X
Randomize eligible subjects		X					
Dispense study drug ^o		X					
Confirm subject takes first dose of study drug (in the clinic)		X					
Confirm study drug dosing each day via handheld device		X	X	X	X	X	X
Return study drug and assess compliance ^l			X	X	X	X	X
Misuse, Abuse, and Diversion Drug Event Reporting System [®] (MADDERS) ^s				X	X	X	X
Record Daily Sleep Interference Scale (DSIS) each morning ⁿ	X	X	X	X	X	X	X
Assess handheld diary compliance		X	X	X	X	X	X
MINI International Neuropsychiatric Interview (MINI)	X		X	X	X	X	X
Fibromyalgia Impact Questionnaire – Revised (FIQR)				X	X	X	X
Patient Reported Outcomes Measurement Information System – Fibromyalgia (PROMIS _{TM}) ^t			X	X	X	X	X
Patient Global Impression of Change (PGI-C) scale					X	X	X
Sheehan Suicidality Tracking Scale (S-STS)	X	X	X ^v	X	X	X	X
Concomitant medications ^q	X	X	X	X	X	X	X
Adverse events ^r	X	X	X	X	X	X	X
Safety follow-up calls							X ^y

^a Subjects will discontinue all concomitant analgesic medications taken for pain related to fibromyalgia. Duration of the period will depend upon the analgesic(s) being discontinued, not to exceed 4 weeks. Subjects not taking any concomitant analgesic medications at Visit 1 may directly begin Week -1 of the Screening Period.

^b ET=Early Termination. Subjects who prematurely discontinue randomized treatment will have Week 12 procedures performed. Diary completion ends the night before the Week 12 visit.

^c Informed consent includes an additional consent for inclusion in a secure, proprietary, research subject database to screen for protocol violators. The main informed consent document may be executed up to 30 days prior to the screening visit. The date the first screening related activity is completed will be considered the subject's screening date. If the subject does not complete the screening visit within 30 days of signing the informed consent document, the subject must be reconsented.

^d Verify subject still meets all inclusion criteria and does not meet any exclusion criteria.

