- Urine pregnancy test, if clinically indicated for females of childbearing potential
- Urine drug test
- Rescue medication return, assessment of appropriate use by inventory of returned tablets, as well as by subject interview
- Study drug return and assessment of compliance by inventory of returned capsules, as well as by subject interview
- Compliance with entry into daily diary of pain intensity and rescue medication use
- PGI-C
- FIQR
- PROMIS_{FM} (sleep disturbance, fatigue profile and physical function)
- [REDACTED]
- Dispensing of study drug – Subjects will be instructed to take one capsule of study drug by mouth once daily
- Re-dispensing/dispensing of rescue medication – Subjects will be reminded not to exceed 3 g/day (one to two 500 mg tablets every 6 hours as needed) for pain related to fibromyalgia
- Subjects will be reminded on how to record their pain score on the device and will also be reminded about appropriate expectations for their participation in a clinical study and the importance of consistently and accurately reporting their pain intensity throughout the study. Review of these educational materials will be repeated for all subjects as refresher training or based on findings of an ongoing blinded data review (e.g., if pain score variability is increased on a subject or site level) via the aLearn[®] portal. On each day until returning to the study site at Week 8/Visit 5, subjects will record the following on the handheld device:
 - At bedtime: average pain intensity and use of rescue medication during the past 24 hours.
 - Upon waking: DSIS and confirm when study drug has been taken

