6.2.8 Treatment Compliance

Treatment compliance will be calculated per visit interval (Visit 2 to Visit 4, Visit 4 to Visit 5, and Visit 5 to Visit 6) as follows:

$$\frac{\text{Total number of capsules dispensed} - \text{Total number of capsules returned}}{(\text{Number of days within the visit interval})} \times 100$$

Total number of capsules dispensed will be obtained as below:

- Visit 2 to Visit 4: the total number of capsules dispensed at Visit 2
- Visit 4 to Visit 5: the total number of capsules dispensed at Visit 4
- Visit 5 to Visit 6: the total number of capsules dispensed at Visit 5

Total number of capsules returned will be obtained as below:

- Visit 2 to Visit 4: the total number of capsules returned at Visit 4
- Visit 4 to Visit 5: the total number of capsules returned at Visit 5
- Visit 5 to Visit 6: the total number of capsules returned at Visit 6

The number of days within the visit interval is obtained as follows:

- Visit 2 to Visit 4: (Date of Visit 4 – Date of first dose of study drug) + 1
- Visit 4 to Visit 5: (Date of Visit 5 – Date of Visit 4)
- Visit 5 to Visit 6: (Date of Visit 6 – Date of Visit 5)

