6.2.17.2 Post-Baseline Weekly Mean NRS Scores

Weekly Mean NRS Scores for Week 12 (and prior weeks) will be obtained based on the subject’s actual Week 12 visit date. If the subject’s Week 12 visit date is within Day 80 to Day 88, then the 7th NRS score for Week 12 will be the corresponding NRS score on the day before the subject’s Week 12 visit date, and the 6th to 1st NRS score for Week 12 will be obtained backwards from this. Thus, the corresponding NRS scores on the last 7 days prior to Week 12 actual visit date will be used for Week 12. Consequently, the Week 11 NRS scores will be obtained by counting 7 days backwards from the 1st NRS score for Week 12, Week 10 NRS scores will be obtained by counting 7 days backwards from the 1st NRS score for Week 11 and continuing up to Week 1. If the subject’s

actual Week 12 visit date is beyond Day 88, then the corresponding NRS score on the day before Day 88 (i.e., Day 87) will be used as the 7th NRS score for Week 12, and the 6th to 1st NRS score will be obtained backwards from this and continuing for each week from Week 11 to Week 1. Meanwhile, if the subject's actual Week 12 visit date is earlier than Day 80, then no Week 12 data will be identified.

Timing of Week 12 Visit	Reference Day (NRS)
Day 80 to Day 88	Count backwards from day before Week 12 visit (Week 12 study day -1)
Day 89+	Count backwards from Day 87 only
Earlier than Day 80	No Week 12 data identified

For subjects that withdraw early or have missing data such that they do not have any data that would fall into the Week 12 windowing, their last non-missing diary day will serve as the anchor; weeks will be counted backwards in 7-day intervals from the last day. For the week ending with this anchor day, study week will be assigned such that the majority of days fall in the nominal week. For example, Week 11 is nominally day 71-77; if a subject's last value is on day 74, the majority of the resulting 7-day window working backwards would be in "Week 11", so their last week would be analyzed as "Week 11" and the subsequent intervals assigned descending weeks working backwards. The following table shows how the last interval will be assigned based on its last day.

Timing of Last Non-Missing Diary	Assigned Week (from which to count backwards)
Day 1 to Day 10	Week 1
Day 11 to Day 17	Week 2
Day 18 to Day 24	Week 3
Day 25 to Day 31	Week 4
Day 32 to Day 38	Week 5
Day 39 to Day 45	Week 6
Day 46 to Day 52	Week 7
Day 53 to Day 59	Week 8

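### A 32-capsule bottle cannot cover a 36-day gap between Visits 5 and 6, so unless leftovers are handed back a few in-window schedules leave adherent subjects without drug at the end of the Week 12 diary week

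*Protocol*

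**What the plan says.** **Supply.** Protocol 8.1: "A four-week supply of study drug will be dispensed at Weeks 0 (baseline), 4, and 8". Dosing is one capsule daily throughout the study. Protocol 8.2 sets the bottle content for Visits 2, 4 and 5: each "will include 32 capsules of NYX-2925 50 mg, NYX-2925 100 mg or matching placebo capsules".

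**Visit windows.** Protocol Table 3 puts Visit 4 at Day 28±4, Visit 5 at Day 56±4 and Visit 6 at Day 84±4, all counted from Day 1.

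**Endpoint week.** SAP 6.2.17.2, for a Week 12 visit on Days 80 to 88: "the corresponding NRS scores on the last 7 days prior to Week 12 actual visit date will be used for Week 12". Protocol Table 3, footnote b: "Diary completion ends the night before the Week 12 visit".

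**Leftovers.** Subjects bring unused drug to each visit (Table 3, footnote l), and the site keeps returned bottles (Protocol 8.5). In Protocol 10.3.2 the study-drug bullet at Visits 4 and 5 reads "Dispensing of study drug – Subjects will be instructed to take one capsule of study drug by mouth once daily", while the next bullet begins "Re-dispensing/dispensing of rescue medication". For the last compliance interval, SAP 6.2.8 takes as capsules dispensed: "Visit 5 to Visit 6: the total number of capsules dispensed at Visit 5". Neither document says whether unused study drug goes back to the subject, or what happens when an interval exceeds 32 days.

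**The concern.** Thirty-two capsules absorb one visit being four days off. They do not absorb an early Visit 5 followed by a late Visit 6, although both visits are compliant. Any shortfall comes at the end of the interval, and the end of this interval is the week that defines the primary endpoint. A subject who did everything the protocol asks could then contribute off-drug pain scores to the Week 12 mean. What is at stake is a small, avoidable dilution of a true effect.

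**Working it through.** **1. The plan's own figures.** 28 daily doses + 4 days of window = 32 capsules. For power, the SAP's inputs (85 per arm, difference 0.73, SD 1.7, one-sided 0.05) give 87.6% by the normal approximation and 87.4% by the two-sample t-test. Both agree with the stated figure of about 88%. The t-test value is the reference below.

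**2. Longest interval.** Let Visit 5 = 56 + a and Visit 6 = 84 + b, with a and b each from −4 to 4. The interval is 28 + b − a, which ranges from 80 − 60 = 20 to 88 − 52 = 36 days. There are 9 × 9 = 81 date pairs.

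**3. Uncovered diary days, no hand-back, every dose taken.** The last pain-diary day is Visit 6 − 1 = 83 + b.

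- *SAP 6.2.8 convention.* The first interval includes both end days (+1) and later intervals have no +1, so each visit day belongs to the interval it closes. The new bottle then covers Visit 5 + 1 to Visit 5 + 32, that is, to Day 88 + a. Uncovered days = max(0, b − a − 5).
- *New bottle opened on the Visit 5 day.* It covers to Day 87 + a. Uncovered days = max(0, b − a − 4).

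| | SAP convention | New bottle on Visit 5 day |
|---|---|---|
| Pairs short by 1 / 2 / 3 / 4 days | 3 / 2 / 1 / 0 | 4 / 3 / 2 / 1 |
| Pairs short, of 81 | 6 | 10 |
| Uncovered days, summed over pairs | 10 | 20 |
| Calendar days affected | 85 to 87 | 84 to 87 |

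If either visit is on its nominal day (a = 0 or b = 0), b − a is at most 4 and nothing is uncovered. All uncovered days lie inside the 7-day Week 12 window.

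**4. Share of subjects and dilution.** The documents give no visit-timing data, so two shapes are assumed, with the two visits' deviations independent: uniform over the 9 days, or triangular with weights 1, 2, 3, 4, 5, 4, 3, 2, 1 (sum 25, so 625 for pairs). Dilution is the mean number of uncovered days divided by 7, on the assumption that the effect vanishes on the first missed day.

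SAP convention:
- Uniform: 6/81 = 7.4% of subjects; dilution 10/81/7 = 1.76%; 0.73 becomes 0.717; power 86.3%.
- Triangular: 15/625 = 2.4%; dilution 21/625/7 = 0.48%; 0.73 becomes 0.726; power 87.1%.

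New bottle on the Visit 5 day:
- Uniform: 10/81 = 12.3%; dilution 20/81/7 = 3.53%; 0.73 becomes 0.704; power 85.2%.
- Triangular: 35/625 = 5.6%; dilution 56/625/7 = 1.28%; 0.73 becomes 0.721; power 86.6%.

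**5. Missed doses.** With independent daily adherence of 95% (an assumption), dilution across both conventions and both timing shapes is 0.1% to 1.4%. At 90% it is 0.04% to 0.5%.

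**6. Does the fix close the gap?** With 36 capsules, 0 of 81 pairs are short for the pain diary under either convention. With 35, one pair is still short if the new bottle starts on the Visit 5 day. With hand-back at Visits 4 and 5, 3 × 32 = 96 capsules exceed the at most 88 doses due through Day 88. Enumerating all 729 Visit 4/5/6 combinations gives no uncovered day.

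**The case against.** **The uncovered days are at or past the end of planned treatment.** Twelve weeks is Days 1 to 84. On the SAP convention every uncovered day is Day 85 or later; on the other, 16 of 20 are, and the remaining 4 are Day 84. So the subject has had essentially all of the planned dosing. This stands. But Protocol 8.1 continues daily dosing throughout the study, and the SAP still averages these days into Week 12.

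**Leftovers may be handed back.** This is decisive if true, and the documents do not forbid it. The stated purpose of bringing drug back is compliance monitoring, and dispensing runs through the IRT, whose rules are not in these documents. Against it are the wording contrast in Protocol 10.3.2, the site's retention of bottles, and a compliance formula with no carry-over. The retention sentence also covers rescue medication, which is re-dispensed, so it is only suggestive.

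**The percentages rest on assumed timing.** If a subject's visit deviations are positively correlated, early-then-late is rarer and every share in step 4 shrinks. Persistence of effect would shrink the dilution too: Protocol section 4 reports "auditory long-term plasticity changes 3 and 7 days after a single dose", though that was in healthy volunteers and was not pain.

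**It would be visible.** Daily dosing confirmation would show the gap, and SAP 6.2.8 would give 32/36 = 89%. True, but seeing it afterwards does not prevent it.

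A reader might infer that subjects will run out of drug in the primary-endpoint week, or that the result is put at risk. The documents support neither. Hand-back is unresolved, at least 71 of the 81 date pairs are fully covered, and the effect is the same in every arm. It can only pull a true difference towards zero and cannot create one.

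**Conclusion.** The point holds as a minor supply gap. If leftover study drug is not handed back, 6 of 81 in-window Visit 5/Visit 6 pairs on the SAP's convention (10 on the alternative) leave a fully adherent subject undosed on a few Week 12 diary days. At most, dilution is about 0.5% to 1.8% and power drops by 0.3 to 1.1 percentage points on the SAP convention. That rests on full adherence, immediate loss of effect and independent visit deviations with assumed timing shapes; missed doses or persistence of effect make it smaller. It would not change how the trial is interpreted. It is worth raising because the correction is cheap at the planning stage.

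**What to change.** **Preferred.** In Protocol 8.2, change the bottle content from 32 to 36 capsules. This works whether or not leftovers are handed back. The cost is 4 more capsules per bottle and a changed capsule count on the label, so stock already packed would need repackaging. If a dose is to be guaranteed on both visit days, use 37.

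**Alternative.** State in Protocol 8.2 and 10.3.2 that counted leftover study drug is re-dispensed at Visits 4 and 5, and change SAP 6.2.8 so that carried-over capsules count as dispensed. The cost is one protocol sentence, one formula change and slightly more accountability work. The formula change is essential. Take a fully adherent subject with Visits 4, 5 and 6 on Days 28, 52 and 88:

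- Visit 4: 32 − 28 = 4 left over.
- Visit 5: 4 + 32 − 24 = 12 left over.
- Visit 6: 12 + 32 − 36 = 8 returned.

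The present formula would report (32 − 8)/36 = 67% instead of 100%.

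Neither option changes the visits, the sample size or the efficacy analysis.
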